## 2.3 RISK/BENEFIT ASSESSMENT

### 2.3.1 KNOWN POTENTIAL RISKS

This study will use commercially-available, FDA-approved allergenic extract for diagnostic testing and commercially-available, FDA-approved allergenic extract for therapeutic use (Mountain Cedar Pollen, ALK-Abelló, Inc., Port Washington, NY 11050; US Government License No. 1256) with sterile saline with 0.4% phenol as a diluent or placebo control. The risks described in the approved product labels are described in the following section. The package inserts are attached in Appendix 1 and Appendix 2.

#### **Immediate and Short-term Risks**

Administration of allergenic extracts for diagnostic testing and AIT has the potential to cause IgE-mediated hypersensitivity reactions in sensitized individuals due to the presence of allergen-specific IgE-bearing mast cells in tissues that are exposed to the environment, such as the dermis and mucosa, where they perform a surveillance function. Physiologic data support the belief that mature, allergen-specific IgE-bearing mast cells are not normally found in the lymph nodes (Liu et al. 2013). Thus, the purpose of this research study is to assess whether intra-lymphatic administration of a commercially-available, FDA-approved allergenic extract for Mountain Cedar allergy is safe and effective. Previous data has shown few and mostly mild reactions following intralymphatic injection of many commercially-available allergenic extracts, with comparable efficacy at much lower doses, but no data for ILIT with allergenic extract of Mountain Cedar pollen has been reported. However, there are significant risks inherent in the administration of any allergenic extract skin testing or immunotherapy.

AIT must only be performed by licensed medical personnel experienced in administering allergenic extracts and trained to provide immediate emergency treatment in the event of a life-threatening reaction. Allergenic extracts may potentially elicit a severe life-threatening systemic reaction, which can rarely result in death (Slater et al., 2012). Patients with unstable asthma or steroid dependent asthmatics and patients with underlying cardiovascular disease are at greater risk to a fatal outcome from a systemic allergic reaction, and thus the treating physician must carefully assess the individual risk and potential benefits for allergen testing and immunotherapy for those patients. This study will exclude patients that, in the opinion of the investigator meet the criteria for increased risk of fatal outcomes outlined in the label information for allergenic extracts. Therefore, emergency measures and personnel trained in their use must be available immediately in the event of such a reaction. The label information indicates that patients should be instructed to recognize adverse reaction symptoms and be observed in the office for at least 30 minutes after skin testing or AIT treatment. This study will include a sixty-minute observation period following ILIT to ensure that delayed hypersensitivity reactions, should they occur, are likely to be

observed in the clinic. Patients will be instructed to contact the physician's office if delayed-onset hypersensitivity symptoms occur.

Invasive medical procedures, including injections may cause some patients to experience pre-procedural anxiety. This may be characterized by feelings of anxiety and related physiologic responses, including increased heart rate, respiration, and/or blood pressure. In most cases, pre-procedural anxiety and the associated symptoms do not require any treatment and resolve spontaneously in less than one hour.

Allergenic extract should be temporarily withheld from patients or the dose adjusted downward if any of the following conditions exist: (1) severe symptoms of rhinitis and/or asthma; (2) infection or flu accompanied by fever; or (3) exposure to excessive amounts of clinically relevant allergen prior to a scheduled injection. Furthermore, immunotherapy should not be initiated during a period of symptoms due to exposure. Since the individual components of the extract are those to which the patient is allergic, and to which he or she will be exposed, typical allergic symptoms may follow shortly after the injection, particularly when the antigen load from exposure plus the injected antigen exceeds the patient's antigen tolerance.

### **Local Reactions**

With diagnostic allergy testing, a positive skin reaction is to be expected in sensitive patients as part of the confirmatory diagnostic process. The positive reaction typically defined as an urticarial wheal with surrounding erythema (resembling somewhat a mosquito bite reaction) larger than the control site. The smallest reaction considered positive is erythema with a central papule at least 5 mm in diameter. In some cases, with no reaction at the control site, erythema can be considered an indication of sensitivity. In general, the size of wheal and erythema response correlates directly with the patient's sensitivity to the allergen. This study will employ histamine as a positive control. Thus, participants in this study can expect to experience at least one urticarial wheal associated with the allergy diagnosis.

For patients receiving AIT injection, some erythema, swelling or pruritus at the site of injection are common, the extent varying with the patient. Such reactions should not be considered significant unless they persist for at least 24 hours. Injections with allergenic extracts in 50% glycerin are known to cause discomfort at the site of the injection.

Local reactions (erythema or swelling) which exceed 4-5 cm in diameter are not only uncomfortable, but also indicate the possibility of a systemic reaction, especially if the dosage is increased. Large, persistent local reactions may be treated by local cold, wet dressings and/or the use of oral antihistamines. They should be considered a warning of possible severe systemic reactions and an indication of the need for temporarily reduced dosages. A mild burning immediately after the injection is to be expected. This usually subsides in 10 to 20 seconds.

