However, if a systemic or anaphylactic reaction does occur, patients will be treated according to the instructions on the label information and the 2015 Joint Practice Parameter Updated for Treatment of Anaphylaxis (Lieberman et al. 2015), as described below. Specifically, adults require an injection of 0.3 mL to 0.5 mL of 1:1,000 epinephrine-hydrochloride intramuscularly or subcutaneously into the lateral thigh (*vastus lateralis* muscle). This should be repeated after five to ten minutes, if necessary. Doses of epinephrine may be repeated as frequently as every 20 minutes thereafter, depending on the severity of the condition and the response of the patient. After administration of epinephrine, profound shock or vasomotor collapse should be treated with volume expanders and vasopressor agents to reverse hypotension. Airway patency should be insured. In case of respiratory obstruction, oxygen should be given by mask and intubation may be necessary. Inhalation bronchodilators and parenteral aminophylline may be required to reverse bronchospasm. Intravenous antihistamine, theophylline and/or adrenal corticosteroids may also be used if necessary after adequate epinephrine and circulatory support has been given. Emergency resuscitation measures and personnel trained in their use must be available immediately in the event of a serious systemic or anaphylactic reaction not responsive to the above measures. Therefore, patients may require cardiopulmonary resuscitation. Rarely are all these measures necessary as epinephrine is usually sufficient to produce a prompt response. However, the physician administering immunotherapy must be prepared in advance for all contingencies. Promptness in the initiation of emergency treatment measures is of utmost importance. Patients experiencing severe reactions may be transferred to a hospital for further treatment. There may be costs to the patient for treatment received in that setting. Severe systemic reactions mandate a decrease of at least 50% in the next dose, followed by cautious increases thereafter. Repeated systemic reactions, even of a mild nature, are sufficient reason for the cessation of further attempts to increase the reaction-causing dose allergenic extracts. Rates of systemic reactions reported in clinical trials of SCIT, SLIT, and ILIT appear similar.

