### 2.3.3 ASSESSMENT OF POTENTIAL RISKS AND BENEFITS

AIT has been an accepted treatment for allergies for more than 100 years and is the only proven disease-modifying therapy. Diagnosis and treatment of allergies using conventional AIT is rarely associated with serious systemic reactions. Allergists conducting diagnosis or immunotherapy treatment must be highly trained in the use of allergenic extracts and the treatment of potentially life-threatening reactions as part of normal clinical practice (Cox et al., 2011).

Confirmation of allergy to mountain cedar pollen will follow the procedures described in the Prescribing Information and the immunotherapy dosing will be customized based on individual patient sensitivity during confirmatory testing. This is in accordance with the normal, FDA-approved clinical use of mountain cedar allergenic extract for AIT.

This study will involve minimal deviations from the normal conditions of use for AIT. AIT requires that allergists must modify and adjust the dose-titration of allergenic extracts using clinical judgment and patient response on the MQT, in accordance with guidance from the approved label (Appendix 1) and the clinical practice guidelines (Cox et al., 2011), as part of their routine care and management of patients in clinical practice. Adjustments to dosing and related safety precautions, as described above for the management of local and systemic reactions, including the management of potential anaphylactic reactions, will not vary significantly from the procedures described in the approved label for the allergenic extract (Appendix 1) and the current, best practice standard of care as described by the AAAAI Practice Parameter for Anaphylaxis diagnosis and treatment (Lieberman et al., 2015).

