### 6.2.4 PREPARATION

Preparation of syringes and, if necessary patient-specific extract dilutions will follow TASC's SOPs and the AAAAI Practice Management Resource Guide, 2014 edition, Allergen Immunotherapy Extract Preparation Manual. Specifically, bulk extracts will be diluted at the investigational drug pharmacy at a standard 1:100th dilution using Sterile Diluent for Allergenic Extracts. Dilutions will be made with sterile disposable syringes using aseptic technique using two sequential, 10-fold dilution processes to achieve the desired concentration for initiation and continuation of immunotherapy. For example, transferring 0.5 mL of a 10,000 PNU/mL extract into 4.5 mL of diluent will yield 5 mL of extract at 1,000 PNU/mL. For weight volume products, a 1:100 w/v dilution may be prepared from a 1:10 w/v by transferring 0.5 mL of the 1:10 w/v to 4.5 mL of diluent. Prepare as many additional serial dilutions as necessary to reach the appropriate concentration.

For patients that display a hypersensitivity reaction to the extract, as defined in section 5.2 (a wheal for allergenic extract greater than that for the positive control), the initial dose will be at an additional 1:10 dilution. For patients that experience a systemic reaction to any ILIT injection, as defined in section 2.3.2, subsequent ILIT injections will be made at a 1:10 dilution from the preceding treatment. Thus, the dosing will be as follows:

Baseline	Not Hypersensitive to Allergenic Extract on MQT				IS HYPERSENSITIVE to Allergenic Extract on MQT			
Injection 1	Inject 0.1 mL of undiluted IP				Inject 0.1 mL of 1:10 diluted IP			
Injection 2	No Systemic Reaction at Injection 1 Inject 0.1 mL of undiluted IP		SYSTEMIC REACTION at Injection 1 Inject 0.1 mL of 1:10 diluted IP		No Systemic Reaction at Injection 1 Inject 0.1 mL of 1:10 diluted IP		SYSTEMIC REACTION at Injection 1 Inject 0.1 mL of 1:100 diluted IP	

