Injection 3	No Systemic Reaction at Injection 2 Inject 0.1 mL of undiluted IP	SYSTEMIC REACTION at Injection 2 Inject 0.1 mL of 1:10 diluted IP	No Systemic Reaction at Injection 2 Inject 0.1 mL of 1:10 diluted IP	SYSTEMIC REACTION at Injection 2 Inject 0.1 mL of 1:100 diluted IP	No Systemic Reaction at Injection 2 Inject 0.1 mL of 1:10 diluted IP	SYSTEMIC REACTION at Injection 2 Inject 0.1 mL of 1:10 diluted IP	No Systemic Reaction at Injection 2 Inject 0.1 mL of 1:100 diluted IP	SYSTEMIC REACTION at Injection 2 Inject 0.1 mL of 1:1,000 diluted IP

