### 6.3 MEASURES TO MINIMIZE BIAS: RANDOMIZATION AND BLINDING

Once enrollment, subjects in this study will be randomized in a 1:1 ratio to receive either ILIT with 1:100 diluted Mountain Cedar pollen allergenic extract or diluent as placebo control. Preparation of the diluted allergenic extract or placebo will be performed by the pharmacy according to the procedures defined in Section 6.2. Neither the patient nor the investigator will know the treatment assignment. Randomization information will be stored in the EDC system. Emergency unblinding is unlikely to be required. Patients receiving AIT are at risk of systemic hypersensitivity reactions and such reactions will be treated according to the procedures outlined in Section 2.3.1 regardless of treatment assignment. Blinding may be imperfect in cases where strong systemic reactions occur, but in previous trials of AIT, injection site reactions and systemic reactions, including anaphylaxis have been reported to occur in both groups, but at a lower rate in the placebo group. Thus, this risk of unblinding due to obvious treatment-related side effects is possible, but not definitive. Dose adjustments will be made by serial dilution following the procedures outlined in Section 6.2 and do not require knowledge of the treatment assignment. The end-of-study assessment will include a question for subjects regarding their belief about which treatment they received. This will be used to assess the maintenance of the study blind.

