### 8.1.1.3 Visit 3 (Treatment Visit 2)

The following procedures will be performed:

- For women of childbearing potential, perform a urine pregnancy test to confirm continued eligibility for the study
- Collect vital signs
- Assess patient for any changes to medical history, including adverse events since the previous visit, resolution of ongoing adverse events from Visit 1, or changes in concomitant medication use
- Perform ILIT procedure following the procedures outlined in detail in section 6.1.2:
  - Identify and select a right-sided superficial inguinal lymph node using ultrasonography
  - Prepare the area for aseptic injection
  - Verify assignment of the subject's assigned vial of allergenic extract or matched placebo
  - Inspect vial for clarity or discoloration
  - For patients that experienced a reaction at a prior injection, prepare a 1:10 or 1:100 dilution using aseptic procedures from the assigned vial and standard Allergenic Extract diluent (phenol-saline), as described in Section 6.2
  - Draw 0.1 mL of allergenic extract from the vial or the 1:10 dilution, as appropriate using a 1 mL syringe.
  - Tighten the patient's skin around the lymph node using thumb, index finger, and middle finger to pull skin taut and allow for controlled placement of the injection volume.
  - Using a sterile 25-gauge or smaller needle, approach the lymph node with the needle at a 90° angle to the skin
  - Insert the needle into the selected lymph node and aspirate the syringe by pulling the plunger slightly to avoid accidental intravenous administration
    - If blood is drawn up, discard and replace the syringe and extract, prepare a new syringe and repeat
  - Slowly inject into the entire volume into the lymph node and during injection, observe the lymph node volume through the skin to confirm injection by visible enlargement.
  - Administer a sterile dressing, if necessary
  - Record injection information in the patient's medical chart
- Collect vital signs every fifteen minutes for one hour (60 minutes) post-injection

- Collect patient-reported pain immediate after and 30 minutes post-injection using the NRS-11
- Record any local or systemic reactions on the TSS worksheet
  - Patients that are stable and do not have any evidence of a systemic reaction will be monitored in the office for sixty (60) minutes post-injection

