#### 8.1.1.4 Visit 4 (Treatment Visit 3)

The following procedures will be performed:

- For women of childbearing potential, perform a urine pregnancy test to confirm continued eligibility for the study
- Collect vital signs
- Assess patient for any changes to medical history, including adverse events since the previous visit, resolution of ongoing adverse events from Visit 2, or changes in concomitant medication use
- Perform ILIT procedure following the procedures outlined in detail in section 6.1.2:
  - Identify and select a right-sided superficial inguinal lymph node using ultrasonography
  - Prepare the area for aseptic injection
  - Verify assignment of the subject's assigned vial of allergenic extract or matched placebo
  - Inspect vial for clarity or discoloration
  - For patients that experienced a reaction at a prior injection, prepare a 1:10 or 1:100 dilution using aseptic procedures from the assigned vial and standard Allergenic Extract diluent (phenol-saline), as described in Section 6.2
  - Draw 0.1 mL of allergenic extract from the vial or the 1:10 dilution, as appropriate using a 1 mL syringe.
  - Tighten the patient's skin around the lymph node using thumb, index finger, and middle finger to pull skin taut and allow for controlled placement of the injection volume.
  - Using a sterile 25-gauge or smaller needle, approach the lymph node with the needle at a 90° angle to the skin
  - Insert the needle into the selected lymph node and aspirate the syringe by pulling the plunger slightly to avoid accidental intravenous administration
    - If blood is drawn up, discard and replace the syringe and extract, prepare a new syringe and repeat
  - Slowly inject into the entire volume into the lymph node and during injection, observe the lymph node volume through the skin to confirm injection by visible enlargement.
  - Administer a sterile dressing, if necessary
  - Record injection information in the patient's medical chart
- Collect vital signs every fifteen minutes for one hour (60 minutes) post-injection
- Collect patient-reported pain immediate after and 30 minutes post-injection using the NRS-11

- Record any local or systemic reactions on the TSS worksheet
  - Patients that are stable and do not have any evidence of a systemic reaction will be monitored in the office for sixty (60) minutes post-injection

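### The 6.2.4 dosing table repeats the same dose after a large, persistent local reaction, which Section 2.3.1 treats as a reason to lower it

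*Protocol*

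**What the plan says.** Section 2.3.1 of the protocol, under Local Reactions, takes erythema or swelling beyond 4-5 cm as a sign that a systemic reaction is possible. It says that common injection-site reactions matter only if they last at least 24 hours. Of large, persistent reactions it says: "They should be considered a warning of possible severe systemic reactions and an indication of the need for temporarily reduced dosages".

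Section 2.3.3 takes this into the study. It refers to "Adjustments to dosing and related safety precautions, as described above for the management of local and systemic reactions" and states that these will stay close to the approved label and to current practice.

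The operative rule is in Section 6.2. Section 6.2.1 names 6.2 as the patient-specific regimen, and Section 6.3 states: "Dose adjustments will be made by serial dilution following the procedures outlined in Section 6.2". The text of 6.2.4 lowers the dose after a systemic reaction. For a patient who is not hypersensitive and has none, the table reads "No Systemic Reaction at Injection 1 Inject 0.1 mL of undiluted IP" for the second injection and "No Systemic Reaction at Injection 2 Inject 0.1 mL of undiluted IP" for the third. It has no entry for local reactions.

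The lists for Treatment Visits 2 and 3 (8.1.1.3 and 8.1.1.4) use a looser trigger, "For patients that experienced a reaction at a prior injection, prepare a 1:10 or 1:100 dilution", and complete the sentence with a reference back: "from the assigned vial and standard Allergenic Extract diluent (phenol-saline), as described in Section 6.2".

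**The concern.** The protocol describes a warning sign and says that it points to a lower dose. It then gives the investigator a dosing table in which that sign has no effect. Followed as written, the table repeats the dose in a patient whom the protocol's own risk section regards as being at possible risk of a severe systemic reaction.

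Systemic safety is the primary objective in Section 3. The favourable risk-benefit statement in 2.3.3 rests partly on dose adjustment for local reactions, so the regimen should deliver that adjustment or the statement should not rely on it.

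**Working it through.** No alpha, power or sample-size figure is involved, and the plan states no number to reproduce. The check traces one patient through the sections: a large, persistent local reaction at an injection, with no systemic reaction at any injection.

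**Next injection, by section**

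- *6.2.4, not hypersensitive:* 0.1 mL undiluted IP is followed by 0.1 mL undiluted IP. Reduction: 0%.
- *6.2.4, hypersensitive:* 0.1 mL of the 1:10 dilution is followed by 0.1 mL of the 1:10 dilution. Reduction: 0%.
- *2.3.1 with 2.3.3:* a temporarily lower dose, amount not stated.
- *8.1.1.3 and 8.1.1.4, read literally:* a 1:10 or 1:100 dilution, since the trigger is not limited to systemic reactions. Read through their reference to Section 6.2, they add nothing to the 6.2.4 rule.

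**Which text is operative.** Sections 6.2.1 and 6.3 both point to 6.2, and 6.2.4 presents its table as the dosing to be given. An investigator following these pointers repeats the dose. The pointers are general: neither mentions local reactions or sets aside 2.3.1 or 2.3.3.

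**Illustrative size.** Section 2.3.1 gives no step for local reactions. Two steps can be borrowed from the systemic-reaction rules, as an assumption:

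- the minimum in 2.3.1: "Severe systemic reactions mandate a decrease of at least 50% in the next dose, followed by cautious increases thereafter". This gives 0.1 × 0.5 = 0.05 mL;
- the 1:10 step in 6.2.4. This gives 0.1 × 0.1 = 0.01 mL of undiluted IP equivalent.

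Three-injection totals for a patient who is not hypersensitive, in mL of undiluted IP:

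- table as written: 3 × 0.1 = 0.300;
- one injection reduced: 0.1 + 0.05 + 0.1 = 0.250 (0.250/0.300 = 83%), or 0.1 + 0.01 + 0.1 = 0.210 (70%);
- both later injections held at the reduced dose: 0.1 + 0.05 + 0.05 = 0.200 (67%), or 0.1 + 0.01 + 0.01 = 0.120 (40%).

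These totals show what a reduction could mean. They do not limit it: the 50% figure is a minimum for severe systemic reactions, and the 1:10 step was also written for systemic reactions.

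**What is recorded.** Reactions within 60 minutes go on the Total Safety Score worksheet and are not reported separately as adverse events (8.3.3.1, 8.3.4). That worksheet (Appendix 3) has no field for diameter or duration, and its key gives any local reaction one point. Later persistence is better covered. Under 8.3.4, patients check the site for seven days and phone in symptoms, and adverse event records carry onset and resolution dates. The lists in 8.1.1.3 and 8.1.1.4 include an adverse event review at the visits for Injections 2 and 3. The main gap is diameter. Section 8.3.8 leaves some doubt about which form is used, because it sends events of interest to the worksheet.

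**The case against.** The best defence is that the table governs and 2.3.1 is background. Section 2.3.1 is introduced as a summary of label risks. Its wording on local reactions is advisory, whereas it uses mandatory wording for severe systemic reactions. Its warning is strongest where the dose is being increased, and this regimen only holds or lowers the dose, starting from a 1:100 dilution. Section 2.3.3 promises closeness to the label, not identity with it, and relies on clinical judgment. Section 7.1 lets the investigator stop treatment at any time. Earlier intralymphatic studies summarised in Section 2.2 reported local reactions that were mild or resolved without treatment.

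Much of this stands. A reader might infer that the protocol leaves open which section governs; 6.2.1, 6.2.4 and 6.3 show that it favours the table. That does not remove the contradiction. It makes repetition of the dose the default after the stated warning sign. The absence of escalation is only a partial answer, because 2.3.1 speaks of lower dosages and not merely of withholding an increase. Judgment and the right to stop may avert harm, but neither says what the next dose is.

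A reader might also infer that the trial has no means of noticing persistent reactions. The follow-up provisions in 8.3.4 and the visit reviews do not support that. Nor do the unqualified visit lists amount to a separate dosing rule: they refer back to 6.2 and are probably shorthand for it.

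**Conclusion.** The contradiction is real and bears on safety. The operative table repeats the dose after a reaction that 2.3.1 links to a reduced one and that 2.3.3 brings within the study's dose adjustments, and no sentence reconciles them. The sponsor should correct it, but it does not undermine the design.

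The number of patients affected cannot be derived from the documents. It is probably small: the glycerin study cited in Section 2.2 found large local reactions infrequent, though with subcutaneous injection. The dose totals rest on borrowed steps and on an assumed number of reduced injections, so they are illustrations only.

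Two further inferences are not supported. One is that the arms would be affected unequally: of the earlier placebo-controlled studies in Section 2.2, one reports more local events with active treatment, while another reports comparable safety scores (mean 0.6 versus 0.4, p = 0.80). The other is that the earlier study of indoor allergens, which kept the concentration unchanged after a moderate local reaction, justifies repeating the dose here. That regimen was escalating, so an unchanged concentration meant a withheld increase, and the account of its dose decreases is incomplete in the available text.

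**What to change.** - **6.2.4:** add a branch to the table. A local reaction that exceeds the 4-5 cm marker and lasts at least 24 hours, without a systemic reaction, leads to a reduced next injection. The existing 1:10 step is one candidate; the sponsor may set another. State whether the reduction covers one injection or all that remain.
- **8.1.1.3 and 8.1.1.4:** name both triggers, a systemic reaction or a large, persistent local reaction, in place of the unqualified term.
- **Case report form:** record the diameter and duration of local reactions at the adverse event review already held at the visits for Injections 2 and 3.

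If the sponsor instead decides on clinical grounds that local reactions do not change the dose in this trial, 2.3.1 and 2.3.3 must say so, and the visit lists should specify systemic reactions. That removes the contradiction in the text but leaves the dosing as it is.

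The cost of the new branch is some rewording, one form item, and a lower allergen dose in what is probably a small number of patients. No extra visits or patients are needed.
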